8.4.3 Exploratory endpoints

The exploratory endpoints for this study are the following:

- Change from baseline (Day -1/1) to Week 10 (Day 69/70) and Week 4 (Day 27/28) in the 24-hour MAGE using CGM system
- Change from baseline (Day -1/1) to Week 10 (Day 69/70) and Week 4 (Day 27/28) using CGM system, in the proportion of time patients who had plasma glucose measurements <70 mg/dL
- Change from baseline (Day -1/1) to Week 10 (Day 69/70) and Week 4 (Day 27/28) using CGM system, in the proportion of time patients who had plasma glucose measurements ≥ 70 mg/dL and ≤ 180 mg/dL
- Change from baseline (Day -1/1) to Week 10 (Day 69/70) and Week 4 (Day 27/28) using CGM system in the proportion of time patients who had plasma glucose measurements >180 mg/dL
- Change from baseline (Day 1) to Week 10 (Day 70) and Week 4 (Day 28) in HbA1c

- Change from baseline (Day -1) to Day 6 of Week 10 (Day 69) and Day 6 of Week 4 (Day 27) in 2-hour PPG (after the breakfast meal)
- Differences between mean daily 24-hour glucose profile during 7-day CGM system assessments during the lead-in period and 7-day CGM system assessments during Week 10.
 - Additionally, the relationship between exenatide exposure (steady-state concentration) and glycemic response (weighted average AUC_{0-24}) on Day 64 and Day 69 of the Week 10 steady-state dosing interval will be explored (SD, MAGE, “Distance travel”, “Energy”)

8.5 Methods for statistical analyses

Analysis of data will be performed after all patients have completed or have been discontinued from the study. In addition, all relevant queries must be answered and the database must be locked 30 days, prior to the analysis.

8.5.1 Analysis of the primary variable(s)

The primary endpoint of 24-hour mean weighted glucose will be obtained by a CGM method and calculated as the AUC from the 24-hour glucose profile, divided by 24 hours. Details on AUC computations for partially missing 24-hour glucose profiles will be described in the SAP. The changes in 24-hour mean weighted glucose from baseline (Day -1/1) to Day 5-6 of Week 10 (Day 69/70) and to Day 6 of Week 4 (Day 27/28) will be analyzed using a maximum likelihood-based mixed model repeated measures (MMRM) method. The MMRM model will include change in 24-hour mean weighted glucose as the dependent variable; treatment, HbA1c stratum ($<8.5\%$ vs. $\geq 8.5\%$), baseline 24-hour mean weighted glucose, week of visit, and treatment-by-week interaction as fixed effects, and patient and error as random effects. All post-baseline measurements (including early termination visits) of the 24-hour mean weighted glucose will be included in the analysis with no imputation of missing data other than that inherent in the MMRM model. An unstructured covariance matrix will be used for the MMRM analysis, unless the model does not converge, in which case the covariance matrix will be decided upon model convergence status and the Akaike information criterion. The least squares (LS) means, standard errors of LS means, and 2-sided 95% confidence intervals (CI) for the mean change within each treatment group and the difference between treatment groups will be presented. P-values will be provided for the comparison between treatment groups. Data normality will be evaluated. If the data require logarithm transformation to meet the normality assumption for statistical modeling, the LS mean and the corresponding 95% CI will be calculated at the log scale, and the geometric mean ratio and its corresponding 95% CI will be calculated by taking the anti-log of the corresponding values within each treatment group and for treatment comparisons. The 2 primary endpoints will be tested sequentially (Week 10 comparison will follow by the Week 4 comparison) and the family-wise Type I error will be controlled between primary and secondary endpoints. See description in Section 8.5.2.

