8.2 Sample size estimate

Approximately 110 patients are expected to be randomized 1:1 to the EQW + metformin XR and placebo + metformin XR treatment arms (55 patients per treatment arm). The assumed dropout rate (30%) was based on a similar study (SHOT study; 20%), and increased by 10% as the present study is of longer duration, with a more demanding visit schedule. Therefore, a minimum of 39 patients per treatment arm would provide the necessary statistical power.

With 39 patients per treatment group, there is a 90% power to detect a difference in change in 24-hour mean weighted glucose of 18 mg/dL at Week 4 between exenatide once weekly and placebo, assuming an SD of 24 mg/dL. As the plasma exenatide concentrations are expected to continuously increase and achieve steady-state around Week 7-8, the treatment effect on glycemic control will be increased, therefore, it is expected that 39 patients per treatment group will provide >90% power for the Week 10 treatment comparison. With this sample size, there is approximately 83% power to detect a treatment difference in change in FPG of 30 mg/dL, assuming an SD of 45 mg/dL, and approximately 80% power to detect a difference in change in 24-hour mean weighted glucose of 32 mg/dL between treatments, assuming an SD of 50 mg/dL.

The above power calculation is based on a 2-sided t-test at $\alpha=0.05$. Family-wise Type I error will be controlled at 0.05 for primary and secondary endpoints by applying a sequential testing process. The hierarchical order is defined in Section 8.5.2.

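### The primary MMRM imposes one baseline slope on Week 4 and Week 10; a baseline-by-week term is a cheap improvement that helps under some dropout patterns but not all

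*Protocol*

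**What the plan says.** Section 8.5.1, repeated in the synopsis, names every fixed effect of the primary MMRM: treatment, HbA1c stratum, baseline 24-hour mean weighted glucose, and then "week of visit, and treatment-by-week interaction as fixed effects". Baseline enters as a main effect only. The covariance matrix is unstructured, and missing values are handled only through the model. What the section leaves to the SAP is the AUC computation for incomplete profiles, not the model terms. Section 8.5.2 carries a similar model over to FPG and 2-hour postprandial glucose, and places Week 10 first in the testing order.

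Section 8.2 says of the period after Week 4 that "the treatment effect on glycemic control will be increased", because exposure is still rising until about Week 7-8. On dropout it says: "The assumed dropout rate (30%) was based on a similar study". Section 3.9.1 adds a glucose-based discontinuation rule during treatment.

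**The concern.** With one slope for both weeks, the model adjusts each week by a compromise between the two true slopes. If the relation of change to baseline is steeper at Week 10 than at Week 4, the Week 10 adjustment is too shallow.

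That is harmless on average while the two arms have the same baseline distribution. It matters when the patients observed at Week 10 differ in baseline between arms. The protocol allows for 30% dropout, relies on the model for the missing values, and has a discontinuation rule driven by glucose. One would expect that rule to remove more placebo patients with high glucose, although this is an inference and not stated. At stake is the estimate that opens the testing hierarchy.

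**Working it through.** **The plan's own figure.** Section 8.2 states that "there is a 90% power to detect a difference in change in 24-hour mean weighted glucose of 18 mg/dL at Week 4". The other inputs it gives are 39 per arm, SD 24 mg/dL and a two-sided t-test at 0.05. The standard error is 24 × √(2/39) = 5.435 and the noncentrality is 18/5.435 = 3.31. Power is 90.5% by noncentral t (91.2% by the normal approximation), so the stated 90% reproduces. For dropout, 39/0.7 = 55.7, against 55 per arm.

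**Parameter count.** Intercept, treatment, stratum, baseline, week and treatment-by-week make 6. With two analysed weeks, baseline-by-week makes 7. This assumes early-termination values are assigned to Week 4 or Week 10 and not to a week level of their own.

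**Hand approximation.** Let b4 and b10 be the true slopes, b the common fitted slope, ρ the residual correlation between weeks, and d the EQW-minus-placebo gap in mean baseline among patients observed at Week 10. With equal residual variances and Week 4 complete,

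bias at Week 10 ≈ [(b10 − b) − ρ(b4 − b)] × d.

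Assume b4 = -0.3, b10 = -0.5, ρ = 0.6, and b at the midpoint, -0.4. The bracket is -0.1 − 0.6 × 0.1 = -0.16. A gap of d = 10 mg/dL then gives -1.6 mg/dL. If high-baseline placebo patients drop out, d is positive and the EQW effect is overstated.

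**Simulation.** Maximum-likelihood MMRM with unstructured covariance, 55 per arm, 1,200 trials per setting, simulation error about 0.15 mg/dL.

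- From the protocol: SD 24 mg/dL (used here as the residual SD), 30% dropout, Week 4 difference 18 mg/dL.
- Assumed: Week 10 difference 18 mg/dL, baseline SD 30 mg/dL, correlation 0.6, Week 4 slope -0.3, all dropout after Week 4, and the same slope change in both arms.

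Week 10 bias in mg/dL, planned model / with the term:

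| Dropout | Week 10 slope -0.5 | Week 10 slope -0.7 |
|---|---|---|
| None | -0.1 / -0.1 | -0.2 / -0.2 |
| Random | +0.2 / +0.2 | +0.1 / 0.0 |
| Placebo, rising with baseline | -1.7 / +0.2 | -3.5 / +0.1 |
| Placebo, rising with Week 4 glucose | -1.4 / -0.3 | -2.2 / -0.2 |
| Opposite directions in the two arms | -3.5 / +0.2 | -7.4 / +0.1 |

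For the planned model, 95% interval coverage in the last three rows is 93%, 94% and 90% with slope -0.5, and 91%, 93% and 75% with slope -0.7. With the term it is 94-96% throughout. A second simulation with the same residual SD, baseline SD and a slope change of 0.2 in both arms gave 1.4 to 2.8 mg/dL for the planned model and about 0 to 0.2 with the term.

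**Chance imbalance.** Without informative dropout, the planned model's error follows baseline imbalance at 0.12 to 0.25 mg/dL per mg/dL. The imbalance has SD 30 × √(2/55) = 5.7 mg/dL, so the shift is about 0.7 to 1.4 mg/dL in a typical trial. It averages to zero over trials.

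**Cost when slopes are equal.** The empirical standard error rises as follows:

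- random dropout: 5.10 to 5.13 (0.6%)
- placebo dropout by Week 4 glucose: 5.30 to 5.34 (0.8%)
- placebo dropout by baseline: 5.45 to 5.54 (1.7%)
- opposite-direction dropout: 5.29 to 5.61 (6.0%)

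The second simulation found at most about 3%.

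**Slope change in the EQW arm only** (-0.3 to -0.5 in EQW, -0.3 throughout in placebo). Week 10 bias, planned / with the term:

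- placebo dropout by baseline: +0.3 / +1.35; in the second simulation 0.0 / +0.8 or +0.4 / +2.0
- both arms by baseline: +1.7 / +1.8
- EQW dropout by baseline: +2.0 / +1.25

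**The case against.** The strongest reply is that a baseline main effect is a legitimate, prespecified choice and nothing in the protocol contradicts it. That stands: this is an improvement, not a mistake. The reply goes on that the protocol's reason to expect change over time, rising exposure, acts only in the EQW arm. A growing mean effect is already covered by treatment-by-week, and a slope change caused by exposure would be a treatment-by-baseline-by-week effect, which an arm-common term does not model. That also stands, and it limits the benefit to slope changes shared by both arms. The protocol neither states nor rules these out.

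A reader might infer four stronger things, none of which the documents support.

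- **The planned model is biased as it stands.** It is not, on average, with complete data or random dropout.
- **The added term secures the Week 10 estimate whenever slopes differ.** It does not when only EQW's slope changes; with placebo dropout it makes the bias larger.
- **The common slope erodes the 90% power.** The 24 mg/dL in Section 8.2 is the SD of change for an unadjusted t-test, so it already contains the baseline-related variance. With baseline SD 30 and a Week 10 slope of -0.5, the residual SD is √(576 − 225) = 18.7 with its own slope and √(576 − 225 + 9) = 19.0 with a common slope of -0.4. Power at 39 per arm is about 98.5% even with the common slope.
- **The term has no downside.** The standard-error costs above show a small one.

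**Conclusion.** The restriction is real and is fixed in the protocol, and relaxing it is cheap. The benefit is conditional on a slope that changes between weeks in both arms and on dropout that depends on glucose differently by arm. Under a baseline SD of 30 mg/dL and slopes of -0.3 and -0.5, the Week 10 bias avoided is roughly 1 to 3 mg/dL, set against a design difference of 18 mg/dL and a standard error of about 5.3. The figures of 3.5 and 7.4 mg/dL for opposite-direction dropout are extremes and not an expected size. All bias sizes rest on slopes, a baseline SD and a correlation that the protocol does not give. Using 24 mg/dL as a residual SD is an approximation that makes the simulated standard errors somewhat large. The sample size is not affected. Priority is low.

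**What to change.** Add baseline 24-hour mean weighted glucose-by-week to the fixed effects of the primary MMRM in Section 8.5.1 and the synopsis. Add the matching endpoint-specific baseline-by-week term to the secondary MMRMs in Section 8.5.2 (for FPG, baseline FPG-by-week). State to which week early-termination values are assigned. Make the change before any unblinded look, including the optional interim analysis in Section 8.5.4.

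The cost is one parameter per model and the standard-error increase shown above. The text should not present the term as protection against a slope change confined to the EQW arm. The HbA1c stratum effect would remain constant over weeks; this change does not address it.

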5.1 Efficacy assessments

5.1.1 Primary efficacy assessment

5.1.1.1 Mean weighted glucose

The primary efficacy assessment will be the 24-hour mean weighted glucose which will be estimated by dividing the area under the 24-hour glucose curve (AUC_{0-24}) by 24 hours and will be expressed in mg/dL. Detailed calculation will be defined in the statistical analysis plan (SAP). The glucose measurements used for assessment of the primary endpoint will be analyzed from the CGM data.

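### An uncriterioned normality check can switch the primary analysis from a mg/dL difference in change to a geometric mean ratio, without redefining the response

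*Protocol*

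**What the plan says.** Section 8.5.1 defines the primary model: "The MMRM model will include change in 24-hour mean weighted glucose as the dependent variable". The covariate is baseline 24-hour mean weighted glucose, with no mention of a log. The model also has treatment, HbA1c stratum, week and the interaction of treatment with week.

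The same paragraph says that normality of the data will be evaluated and continues: "If the data require logarithm transformation to meet the normality assumption for statistical modeling", LS means and confidence intervals are obtained after logging. The reported summary then changes too: "the geometric mean ratio and its corresponding 95% CI will be calculated by taking the anti-log of the corresponding values within each treatment group". The treatment comparison is handled in the same way. The synopsis has the same wording. Neither place gives a test, a threshold, the quantity to be checked (raw values or residuals) or the time of the check relative to unblinding.

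Other parts of the protocol that bear on this:
- Section 5.1.1.1: the measure is AUC over 24 hours divided by 24 and "will be expressed in mg/dL", so it is always positive.
- Section 8.2: the trial is sized for a "difference in change in 24-hour mean weighted glucose of 18 mg/dL at Week 4", with an SD of 24 mg/dL.
- Section 8.5.2: the Week 10 primary comparison is the first step of the sequential testing procedure.
- Section 8.5.4: the optional interim analysis is built on the mean treatment difference in change from baseline at Week 10 and projects significance of the final primary comparison.

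**The concern.** There are two linked problems.

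First, the fallback does not fit the model it modifies. The only response named is a change score, and a fall in glucose, the effect the trial looks for, is a negative change with no logarithm. To run the fallback, an analyst has to supply a new response and decide how baseline enters.

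Second, and more important, the switch depends on the data and has no rule. Its outcome decides whether the primary estimate is a difference of mean changes in mg/dL or a ratio of geometric means. These are different quantities with different tests. The Week 10 p-value decides whether anything later in the hierarchy may be tested, so the choice of scale affects the whole confirmatory sequence. Because FPG and 2-hour mean weighted PPG use a similar MMRM, the ambiguity may carry over to them.

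**Working it through.** **Step 1. Reproduce the protocol's own figure.** Inputs from section 8.2: 39 per arm, difference 18 mg/dL, SD 24 mg/dL, two-sided alpha 0.05, t-test.

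- Noncentrality = 18 / (24 × √(2/39)) = 18 / 5.435 = 3.312, with 76 degrees of freedom and critical value 1.992.
- Power = 90.5% (noncentral t); normal approximation Φ(3.312 − 1.960) = 91.2%. The stated 90% reproduces.

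The planned power therefore belongs to the untransformed change in mg/dL. Nothing in section 8.2 refers to a ratio.

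**Step 2. How often would the stated response have no logarithm?** The protocol gives no placebo mean change, so call it m and vary it. Assume normal changes with SD 24 and an EQW mean of m − 18.

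- Placebo share below zero: Φ(−m/24)
- EQW share below zero: Φ((18 − m)/24)
- Overall share: the average of the two, given 1:1 allocation

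| Assumed m (mg/dL) | Placebo | EQW | Overall |
|---|---|---|---|
| +18 | 22.7% | 50.0% | 36.3% |
| +9 | 35.4% | 64.6% | 50.0% |
| 0 | 50.0% | 77.3% | 63.7% |
| −10 | 66.2% | 87.8% | 77.0% |
| −18 | 77.3% | 93.3% | 85.3% |

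The chance that all 78 changes (39 per arm) are positive is below 10⁻¹⁵ at every m from −18 to +18. A log of the stated response could not be used anywhere in this range.

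**Step 3. Is there a reading that works?** Yes. Glucose itself is always positive, so log(post) − log(baseline) always exists. The anti-log of its mean within an arm is a geometric mean ratio to baseline, and the anti-log of the difference between arms is a ratio of those ratios. With log(baseline) as covariate, modelling log(post) or log(post/baseline) gives the same treatment contrast. This reading needs a new response and a logged baseline, neither of which section 8.5.1 states.

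**Step 4. What could the open choice of scale cost?** As an upper bound, suppose that under no treatment effect the smaller of the two p-values were always taken. This was simulated with a baseline-adjusted ANCOVA at one visit, SD of change 24, 39 to 55 per arm and normal or skewed errors. Baseline mean (170 to 200 mg/dL) and SD (25 to 40 mg/dL) are assumptions, not protocol figures. Type I error rose from about 5% to between 5.6% and 6.5%, and the two scales disagreed on significance in about 2% of simulated trials.

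**The case against.** The strongest reply is that the protocol never says the log is taken of the change. It says the data. The paragraph opens with 24-hour mean weighted glucose, which is positive, and a geometric mean ratio within an arm makes natural sense only as post-baseline over baseline. That points to logging glucose and taking the change on the log scale, which can be computed. This stands. A reader might infer that the geometric mean ratio cannot be computed at all, or that patients who improve would be lost from the analysis; the text does not support either. Both follow only if the log is applied literally to the change score.

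It can also be said that naming the logged variable, the scale of the covariate and the normality check is normal SAP content, and the SAP is not shown. For the name of the logged variable taken alone, this is right, and that alone would not be a finding. It does not answer the main point. The protocol does not merely leave the switch open; it fixes one. The same paragraph sends partially missing glucose profiles to the SAP but does not send this rule there.

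Finally, the trigger is normality and not the treatment result, and section 8.1 keeps analysis personnel blinded until database lock. This limits the risk of a deliberate choice. The protocol does not, however, say that the check is made before unblinding, so some discretion after seeing data remains.

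**Conclusion.** The point holds as a badly fixed rule in a conditional fallback. The untransformed MMRM in mg/dL is clearly the default and is not in question. What is wrong is that a check without a criterion can replace it as the primary analysis, on a response and covariate that the text does not define, while the sample size and the interim projection concern the mean difference in change. If the final test moved to the log scale, the interim projection would be for a different test.

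The size is modest. The Type I error figures in the working are a ceiling under opportunistic choice and assumed baseline values, not an expected inflation. The share of negative changes illustrates why the change score cannot be logged. A reader might infer that half or more of the patients would be affected, but this is not a protocol figure: the overall share reaches 50% only if the placebo mean change is about +9 mg/dL or lower, and that mean is not given.

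This is a cheap improvement, not a flaw in the main analysis.

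**What to change.** In section 8.5.1 and the synopsis:

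1. State that the MMRM of the untransformed change in mg/dL is the sole primary analysis at Weeks 10 and 4, and that its p-values alone feed the testing hierarchy.
2. Delete the normality-triggered switch.
3. Prespecify a sensitivity analysis: MMRM of log(24-hour mean weighted glucose) at Weeks 4 and 10 with log(baseline) as covariate and otherwise the same terms, back-transformed to a ratio of geometric means with its 95% confidence interval. It is reported whatever the distribution looks like.
4. Say whether the same rule applies to the secondary endpoints that use the similar model. If the SAP already settles any of this, align the protocol wording with it.

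The cost is a few sentences. No patient procedure changes, and the planned power is untouched because it was computed for the mg/dL analysis. The downside is a possible small loss of efficiency if the data are strongly skewed. With about 39 to 55 patients per arm, a comparison of means tolerates moderate non-normality.

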8.5.2 Analysis of the secondary variable(s)

Intra-patient difference and variability of the 24-hour weighted mean glucose between Day 1 and Day 6 of Week 10 will be calculated and presented descriptively; no hypothesis testing will be performed.

The change in FPG from baseline (Day 1) to Day 6 of Week 10 (Day 70) and Day 6 of Week 4 (Day 28), and the change in 2-hour mean weighted PPG (after the breakfast meal) from baseline (Day -1) to Day 6 of Week 10 (Day 69) and Day 6 of Week 4 (Day 27) will be analyzed using a similar MMRM model as the one described for the primary endpoints; except for the analysis of the endpoint of FPG, the baseline FPG will replace the baseline 24-hour mean weighted glucose as one of the fixed effects.

The change in HbA1c from baseline (Day 1) to Day 6 of Week 10 (Day 70) will be analyzed using an analysis of covariance (ANCOVA) model with treatment as a factor and baseline HbA1c as a covariate.

In order to control the family-wise Type I error, a sequential testing procedure will be implemented. In the hierarchical testing order, the primary endpoints of 24-hour mean weighted glucose at Week 10 will be tested first, followed by 24-hour mean weighted glucose at Week 4, then the secondary endpoints: FPG at Week 10, 4-hour mean weighted glucose at Week 10, then FPG at Week 4, and 4-hour mean weighted glucose at Week 4.

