5.1.2 Secondary efficacy assessments

5.1.2.1 Postprandial glucose

Secondary assessments including the 2-hour mean weighted PPG and 2-hour PPG, (2 hours after the breakfast meal) will be obtained during blood draws for glucose measurements after the standardized breakfast during the onsite monitoring visits on Day -7, Day 22, and Day 64 (3 day window) and will be processed at the central laboratory. The 2-hour mean weighted PPG will be estimated by dividing the area under the 2-hour glucose curve by 2 hours. Detailed calculation will be defined in the SAP.

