8.5.3 Analysis of the exploratory variable(s)

The MAGE will be calculated for each patient by taking the arithmetic mean of blood glucose increases or decreases (from blood glucose nadirs to peaks or vice versa) when both ascending and descending segments exceed the value of 1 SD of the blood glucose concentration in a 24 hour period. The proportion of time that patients had plasma glucose measurements <70 mg/dL, ≥ 70 mg/dL and ≤ 180 mg/dL, and >180 mg/dL will be calculated as the time period the glucose level falls into the pre-specified criteria, divided by the total time period. Detailed calculation will be described in the SAP.

Tertiary endpoints will be analyzed using a similar MMRM model to the primary and secondary endpoints, with the baseline value of the dependent variable included as a fixed effect factor.

Daily 24-hour glucose profile collected during the 1 week lead-in period and during Week 10 will be summarized descriptively and plotted. The difference and/or similarity will be discussed.

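### As written, the model for change in 2-hour mean weighted PPG adjusts for baseline 24-hour CGM glucose and not for baseline PPG, which costs precision

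*Protocol*

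**What the plan says.** Section 8.5.2 of the protocol, repeated in the synopsis, treats two secondary endpoints in one sentence: change in FPG and "the change in 2-hour mean weighted PPG (after the breakfast meal) from baseline (Day -1) to Day 6 of Week 10 (Day 69"), together with the matching Week 4 change. Both "will be analyzed using a similar MMRM model as the one described for the primary endpoints".

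Section 8.5.1 fixes the covariates of that primary model. Besides treatment and HbA1c stratum they include "baseline 24-hour mean weighted glucose, week of visit, and treatment-by-week interaction as fixed effects".

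The sentence in 8.5.2 then ends with a single exception, for the FPG endpoint: "the baseline FPG will replace the baseline 24-hour mean weighted glucose as one of the fixed effects". Nothing equivalent is said for PPG.

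Other endpoints are handled differently. HbA1c gets an ANCOVA "model with treatment as a factor and baseline HbA1c as a covariate". Section 8.5.3 models the tertiary endpoints "with the baseline value of the dependent variable included as a fixed effect factor".

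Baseline PPG is collected. Section 5.1.2.1 takes PPG from central-laboratory blood samples "after the standardized breakfast during the onsite monitoring visits on Day -7, Day 22, and Day 64".

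**The concern.** PPG is the odd one out. The primary endpoint, FPG, HbA1c and the tertiary endpoints are each adjusted for their own baseline. If tertiary in 8.5.3 means the exploratory list of 8.4.3, then the exploratory 2-hour PPG gets its own baseline, while the higher-ranked 2-hour mean weighted PPG from the same meal test does not. The covariate it gets instead is a different quantity: interstitial glucose over 24 hours around Day -1/1, against laboratory plasma glucose over 2 hours after a standard breakfast. No reason is given.

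A change score subtracts baseline with a slope of 1. If the true regression of follow-up on baseline has a slope below 1, the subtraction over-corrects: baseline noise and regression to the mean stay in the outcome. Adjusting for the endpoint's own baseline removes this. Adjusting for a correlated proxy removes only part of it. At stake are the standard error of the PPG treatment effect and how far the estimate moves when the arms happen to differ in baseline PPG. With about 39 completers per arm, such differences are to be expected.

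**Working it through.** **The plan's own power figures (Section 8.2).** Inputs: 39 per arm (55 × 0.7 = 38.5), two-sided alpha 0.05. Noncentrality = difference / (SD × √(2/39)).

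| Difference / SD (mg/dL) | Stated power | Normal | Noncentral t |
|---|---|---|---|
| 18 / 24 | 90% | 91.2% | 90.5% |
| 30 / 45 | about 83% | 83.7% | 82.8% |
| 32 / 50 | about 80% | 80.7% | 79.7% |

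All three reproduce. They are t-tests on change, with no covariate. The protocol states no figure for the PPG covariate.

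**Residual variance under each model.** Let ρ be the correlation of baseline with follow-up PPG, r that of baseline PPG with baseline 24-hour glucose, and c that of baseline 24-hour glucose with follow-up PPG. With unit variances at both times:

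- change alone: 2(1 − ρ)
- written model (24-hour glucose as covariate): 2(1 − ρ) − (r − c)²
- own-baseline model: 1 − ρ²

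Written minus own-baseline is (1 − ρ)² − (r − c)². If 24-hour glucose predicts follow-up PPG only through baseline PPG, c = rρ and the difference is (1 − ρ)²(1 − r²), which is never negative. The variance ratio is then

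[2 − r²(1 − ρ)] / (1 + ρ).

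**Numbers.** The documents give no correlations. Assumed ranges: ρ 0.3-0.8, r 0.5-0.85. For power I borrow the 32 / 50 line as a stand-in and take 50 as the SD of change.

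| ρ | r | Ratio, written / own | Residual SD, written / own | Power, written / own |
|---|---|---|---|---|
| 0.3 | 0.5 | 1.40 | 47.8 / 40.3 | 83.2% / 93.3% |
| 0.5 | 0.7 | 1.17 | 46.8 / 43.3 | 84.6% / 89.7% |
| 0.7 | 0.7 | 1.09 | 48.1 / 46.1 | 82.6% / 85.7% |
| 0.8 | 0.85 | 1.03 | 48.2 / 47.4 | 82.6% / 83.7% |

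Example at 0.5 and 0.7: (2 − 0.49 × 0.5) / 1.5 = 1.755 / 1.5 = 1.17. Over the whole grid, power is 81-90% as written and 84-93% with own baseline. A simulation of 8,000 trials at 0.5 and 0.7 gave a variance ratio of 1.18, power of 84.7% against 90.2%, and mean estimates of −32.1 and −32.3 for a true −32. Neither model is biased on average.

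**Sensitivity to the simplification.** Let 24-hour glucose carry information of its own: c = 0.8ρ to 1.0ρ, ρ 0.3-0.7, r 0.6-0.8. Own-baseline variance is then 0.695-0.940 of the written model's, so the written variance is about 6-44% larger. The corners are 0.91 / 1.31 (ρ 0.3, r 0.6, c 0.3) and 0.51 / 0.5424 (ρ 0.7, r 0.8, c 0.56).

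**Chance imbalance.** Suppose the arms differ by one standard error in the part of baseline PPG that 24-hour glucose does not explain. The written estimate then shifts by (1 − ρ) × s × √(1 − r²) × √(2/39), with s = 50 / √(2(1 − ρ)). At 0.5 and 0.7: 0.5 × 50 × 0.714 × 0.226 = 4.0 mg/dL. Across the grid it is about 2-6 mg/dL. A change score with no covariate shifts by 3.6-6.7 for a one-standard-error difference in baseline PPG itself. The proxy therefore leaves √(1 − r²), or 53-87%, of that shift.

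These are single-visit calculations and omit the HbA1c stratum.

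**The case against.** The strongest reply is that this is a drafting slip. The text says similar, not identical, and own-baseline adjustment is the habit elsewhere, so an SAP could put it right. It probably is a slip. But the protocol does not defer the covariate: it states the rule and names one exception. An SAP that follows it inherits the fault, and one that departs from it contradicts the protocol.

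The second reply is that the harm is modest, and this stands. Three stronger readings are tempting, and the documents do not support them:

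- *That chance imbalance goes uncorrected, or that the comparison is biased.* The change score already subtracts baseline PPG, and both the 24-hour glucose covariate and the HbA1c stratum absorb some of the rest. Not properly corrected is the exact description. Randomisation keeps the estimate unbiased on average, and type I error is unaffected.
- *That PPG holds two places in the alpha-controlled sequence.* Section 8.5.2 and the synopsis name 4-hour mean weighted glucose there, a term defined nowhere in the protocol. PPG is the only other comparative endpoint listed in 8.4.2, so the inference is natural, but it remains an inference.
- *That power for PPG is 80% as planned.* Section 8.2 labels the 32 / 50 line as 24-hour mean weighted glucose. Even as a stand-in, an SD of change of 50 means that the written model already gains something from its proxy.

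The HbA1c stratum, left out of the calculations, may narrow the gap further.

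**Conclusion.** The point holds as a loss of efficiency and of conditional balance on a listed secondary endpoint. Under the assumed correlations the written model's variance is about 3-40% larger than with baseline PPG, and about 17% at the middle values. The loss is small when both correlations are high. The direction is firmer than the size: own-baseline adjustment is at least as precise unless r − c exceeds 1 − ρ in absolute value, that is, unless 24-hour glucose tracks baseline PPG much more closely than it tracks follow-up PPG. The power figures are illustrative only, because they borrow a line that the protocol assigns to another endpoint.

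**What to change.** In the synopsis and in Section 8.5.2, replace the FPG-only exception with one rule: *for FPG and for 2-hour mean weighted PPG, the baseline value of the endpoint itself replaces baseline 24-hour mean weighted glucose as a fixed effect.* Name this one model; offering a choice between replacing the CGM covariate and adding to it would leave the analysis open.

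Define baseline PPG as the value from the pre-treatment meal test, which Section 5.1.2.1 and Table 2 place on Day -7. Sections 8.4.2 and 8.5.2 label the PPG baseline Day -1, and the follow-ups Day 27 and Day 69 where 5.1.2.1 has Day 22 and Day 64. These labels must be reconciled.

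The cost is one clause in two places plus the day labels, with no new data or visit. No patient is lost, because a patient without baseline PPG has no change score in either model. Make the change before any treatment codes are released for analysis.
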